6.5.2.1 Liver Safety Assessment

The liver safety assessments will be summarized by the categories below based on the measurements from Alkaline Phosphatase (ALP), Alanine Transaminase (ALT), total

bilirubin, Aspartate Transaminase (AST) and their combination. These parameters will be based on measurements from a central laboratory.

The subject's highest value during the investigational period (from day of first dose of study drug until last dose of treatment period + 1 day) will be used.

- ALT > 3xULN, > 5xULN, > 8xULN, > 10xULN, >20xULN
- AST > 3xULN, > 5xULN, > 8xULN, > 10xULN, > 20xULN
- ALT or AST > 3xULN, > 5xULN, > 8xULN, > 10xULN, >20xULN
- ALP > 1.5 xULN
- Total Bilirubin >2xULN
- (ALT or AST > 3xULN) and Total Bilirubin > 2xULN
- (ALT or AST > $3 \times ULN$) and Total Bilirubin > $1.5 \times ULN$
- (ALT or AST > 3xULN) and ALP< 2xULN and Total Bilirubin > 2xULN

The last 2 criteria where 2 or more parameters are evaluated will be with the measurements on the same day or up to 1 day apart. The denominator for each criterion will be the number of subjects who have at least one value during the double-blind investigational period. The number and percentage of subjects meeting the criteria during the double-blind investigational period will be summarized by treatment group.

Due to COVID-19, patients might not be able to visit the clinical site and have clinical laboratory tests taken at the clinical site and evaluated by the central laboratory, in this case clinical laboratory tests can be taken by a local laboratory. The liver biochemistry safety assessments will be summarized including central and locally collected laboratory data due to COVID-19. This analysis is considered the primary analysis for the liver safety assessments.

The secondary analysis for liver biochemistry will be repeated by the data evaluated by the central laboratory but excluding the data that are impacted by COVID-19, which include the data recorded after the subjects were diagnosed of COVID-19, after study drug discontinuation due to COVID-19, during dose interruption due to COVID-19, and visits that are out of protocol window or data collected via home visits due to COVID-19 recorded in the eCRF.

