11. Subject has active liver disease, jaundice, elevated liver aminotransferases (ALT or AST), elevated total or direct bilirubin (DBL), elevated International Normalized Ratio (INR), or elevated alkaline phosphatase (ALP). Patients with mildly elevated ALT or AST up to 1.5 times the upper limit of normal (ULN) can be enrolled if total and DBL are normal. Patients with mildly elevated ALP (up to $1.5 \times$ ULN) can be enrolled if cholestatic liver disease is excluded and no cause other than fatty liver is diagnosed. Patients with Gilbert's syndrome with elevated TBL may be enrolled as long as DBL, hemoglobin, and reticulocytes are normal.
12. Subject has creatinine $> 1.5 \times$ ULN; or estimated glomerular filtration rate using the Modification of Diet in Renal Disease formula ≤ 59 mL/min per 1.73 m^2 at the screening visit.
13. Subject has a history of suicide attempt or suicidal behavior within the last 12 months or has suicidal ideation within the last 12 months (a response of "yes" to questions 4 or 5 on the suicidal ideation portion of the Columbia-Suicide Severity Rating Scale [C-SSRS]),

or who is at significant risk to commit suicide, as assessed by the investigator at screening and at the time of visit 2 (randomization).

14. Subject has previously been enrolled in a clinical trial with fezolinetant.
15. Subject is participating concurrently in another interventional study or participated in an interventional study within 28 days prior to screening, or received any investigational drug within 28 days or within 5 half-lives prior to screening, whichever is longer.
16. Subject is unable or unwilling to complete the study procedures.
17. Subject has any condition which, in the investigator's opinion, makes the subject unsuitable for study participation.
18. This criterion has been removed.
19. This criterion has been removed.
20. Subject has had a partial or full hysterectomy.

Waivers to the exclusion criteria will **NOT** be allowed.

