5 TREATMENTS AND EVALUATION

5.1 Dosing and Administration of Study Drug(s) and Other Medication(s)

5.1.1 Dose/Dose Regimen and Administration Period

Subjects will be screening up to 35 days prior to randomization. Informed consent will be obtained prior to randomization and before any study-related procedures are performed.

Subjects will be assigned study drug as a kit containing either fezolinetant or placebo at visits indicated in the schedule of assessments. Study drug intake will be done with a glass of room temperature tap water in the morning. The first intake of study drug will take place at the study site on day 1 (visit 2) under the supervision of the study staff.

On study visit days (except for EOT/ED week 52 [visit 15]) study drug will be taken at the study site, under the supervision of the study staff, after collection of predose blood samples. On all other days throughout the treatment period, subjects will be instructed to take their dose of study drug at home with water, in the morning.

In the event of a missed dose, the subject should skip the missed dose and continue with the next scheduled dose.

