- ALT or AST $> 3 \times$ ULN and TBL $> 2 \times$ ULN or INR $> 1.5 \times$ ULN, and INR ;
- ALT or AST $> 3 \times$ ULN with the appearance of fatigue, nausea, vomiting, right upper quadrant pain or tenderness, fever, rash and/or eosinophilia ($> 5\%$ increase above baseline).

Subjects who develop a signal for liver injury will be monitored every 2 to 4 weeks if the study drug is discontinued. If the subject remains on study drug, they will be closely monitored for liver biochemistry results.

Subjects with a signal of elevated ($> 3 \times$ ULN) transaminases will have pharmacokinetic samples drawn in addition to repeat blood draws for liver biochemistry monitoring. These samples can be held for potential analysis based on the subject’s clinical outcome.

In addition, if close monitoring for a subject with moderate or severe hepatic laboratory tests is not possible, study treatment should be discontinued.

***Hy's Law Definition:** Drug-induced jaundice caused by hepatocellular injury, without a significant obstructive component, has a high rate of bad outcomes, from 10 to 50% mortality (or transplant).

The 2 "requirements" for Hy's Law are:

1. Evidence that a drug can cause hepatocellular-type injury, generally shown by an increase in transaminase elevations higher $3 \times \text{ULN}$ ($2 \times \text{ULN}$ elevations are too common in treated and untreated patients to be discriminating).
2. Cases of increased bilirubin (at least $2 \times \text{ULN}$) in people with concurrent transaminase elevations to at least $3 \times \text{ULN}$ (but it is almost invariably higher) and no evidence of intra- or extra-hepatic bilirubin obstruction (elevated ALP) or Gilbert's syndrome [Temple, 2006].

FDA Guidance for Industry titled "Drug-induced Liver Injury: Premarketing Clinical Evaluation" issued by the FDA on July 2009:

FDA Guidance for Industry:

1. The drug causes hepatocellular injury, generally shown by a higher incidence of 3-fold or greater elevations above the ULN of ALT or AST than the (nonhepatotoxic) control drug or placebo.
2. Among trial subjects showing such AT elevations, often with ATs much greater than $3 \times \text{ULN}$, one or more also show elevation of serum TBL to $> 2 \times \text{ULN}$, without initial findings of cholestasis (elevated serum ALP).

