6.5 Analysis of Safety

Overall long-term safety of fezolinetant and the effect of fezolinetant on endometrial health will be the primary objective of this study. The safety assessments include adverse events, laboratory assessments, vital signs, C-SSRS, ECG, endometrial health assessment and imaging (mammogram, DXA, TVU). In all analysis of safety, the treatment group includes placebo, fezolinetant 30mg, fezolinetant 45mg and fezolinetant total will be presented by treatment group for SAF, unless specified otherwise. For analyses by visit, the analysis windows from Section 6.10.1 will be applied. Except for adverse events and follow-up visit data, only data up to one day after the last dose date will be considered for the analyses.

The baseline value for safety endpoint will be the last non-missing value taken on or prior to first dose of study drug unless otherwise noted.

Primary Safety Variables

- Frequency and severity of AEs.
- Percentage of subjects with endometrial hyperplasia.
- Percentage of subjects with endometrial cancer.

Secondary Safety Variables

- Change from baseline in endometrial thickness at 12 months.
- Percentage of subjects with disordered proliferative endometrium.
- Change from baseline in bone mass density (BMD) and trabecular bone score (TBS) at hip and spine at 12 months.
- Change from baseline to each timepoint in vital signs: sitting systolic and diastolic blood pressure and pulse rate.

- Change from baseline to each timepoint in laboratory tests: hematology, biochemistry and urinalysis.
- C-SSRS at each timepoint.
- Change from baseline to each timepoint in ECG parameters

Exploratory Safety Variables

- Change from baseline to specified time points in serum concentrations of sex hormones and sex hormone-binding globulin (SHBG) (week 4, 12, 24, 52 and 55).
- Plasma concentration of fezolinetant and the fezolinetant metabolite ESN259564 at specified timepoints (week 4, 12, 24 and 52).

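### The SAP liver table opens its on-treatment window on Day 1, so a pre-dose baseline bilirubin can be counted as an on-treatment finding, and no row takes account of baseline

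*SAP*

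**What the plan says.** **The liver table.** SAP 6.5.2.1 bases each row on "The subject's highest value during the investigational period (from day of first dose of study drug until last dose", with the window closing one day after the last dose. The rows are fixed multiples of ULN for ALT, AST, ALP and TBL, plus three combined rows that pair ALT or AST > 3 × ULN with TBL > 2 × ULN, TBL > 1.5 × ULN, or TBL > 2 × ULN with ALP < 2 × ULN. The denominator is every woman with at least one value in the window. No row depends on baseline or on Gilbert's syndrome.

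**Baseline and Day 1.** SAP 6.5 states: "The baseline value for safety endpoint will be the last non-missing value taken on or prior to first dose of study drug". Protocol Table 1 schedules clinical laboratory tests at Visit 2 (Day 1). Protocol 5.1.1 says that on visit days other than the end-of-treatment visit the drug is taken "under the supervision of the study staff, after collection of predose blood samples". In SAP 6.10.1 the first post-baseline laboratory window is Day 2 to 22.

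**Entry limits.** Exclusion 11 (Protocol 3.3) says "Patients with mildly elevated ALT or AST up to 1.5 times the upper limit of normal (ULN) can be enrolled", provided total and direct bilirubin are normal, and it caps ALP at 1.5 × ULN. For bilirubin it says "Patients with Gilbert's syndrome with elevated TBL may be enrolled as long as DBL, hemoglobin, and reticulocytes are normal", and gives no upper limit for TBL.

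**The concern.** One blood sample plays two roles. In the by-visit summaries the Day 1 draw is the baseline. In the liver table the same draw can supply the on-treatment maximum. A woman whose only TBL above 2 × ULN was measured before her first dose would be counted as having reached that level on study drug.

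Liver injury is classed as an important potential risk (Protocol 1.5), and the phase 2b study had no case of TBL > 2 × ULN (Protocol 2.2.2). Where the true count may be close to zero, one or two women with pre-existing values can change how the row reads. The rest of SAP 6.5.2 does not separate them. The shift table uses only low, normal and high, so a woman above the normal range at baseline and on treatment shows as no change whether she stayed at 2.1 × ULN or rose from 1.2 to 2.1. Gilbert's syndrome is also not among the liver-table subgroups in SAP 6.5.8.

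**Working it through.** **Step 1: is the Day 1 sample inside the window?** The window opens on the day of first dose, and chemistry is scheduled that day. The visit-day rule puts the dose after the blood draw, and the baseline definition takes the last value on or before first dose. The Day 1 sample is therefore normally pre-drug, the baseline, and inside the window. SAP 6.10.1 keeps it out of the post-baseline visits, so the SAP's two conventions differ.

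**Step 2: which rows can a permitted entry value reach?**
- ALT/AST: entry up to 1.5 × ULN, lowest cut > 3 × ULN. Not reached.
- ALP: entry up to 1.5 × ULN, cut > 1.5 × ULN. Not reached.
- TBL: no entry ceiling in Gilbert's syndrome, cut > 2 × ULN. Can be reached.
- Combined rows: the transaminase half is not reached; the bilirubin half can be.

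The ALT, AST and ALP rows are thus exposed only if the Day 1 value differs from the screening value.

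**Step 3: timing in the combined rows.** SAP 6.5.2.1 applies its same-day (or one day apart) rule to the last two criteria. Protocol 7.6.2 listed two combined rows; the SAP lists three. Read literally, the first combined row (ALT or AST > 3 × ULN with TBL > 2 × ULN) has no timing rule, so a pre-dose Day 1 TBL could pair with an ALT rise months later. In the other two, pre-existing bilirubin contributes mainly by staying raised on treatment.

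**Step 4: size.** The documents give neither the number of women with Gilbert's syndrome nor the share above 2 × ULN before drug. Call that share p and vary it over 0.1% to 0.9%, the rates used in SAP section 3. That section's probability of at least one event is 1 − (1 − p)^580. At p = 0.1% this gives 44.03%, and at 0.9% it gives 99.47%, both as printed; all 27 cells of the table reproduce.

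With n = 580 per arm and 1740 in total, the expected counts are 580p and 1740p. The chance that two arms differ by two or more such women is the sum of b(i)·b(j) over |i − j| ≥ 2, where b is the binomial(580, p) probability. As a plausibility check, the last column is (1 − p)^352, the chance of no case among the 352 women dosed in phase 2b.

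| Assumed p | Per arm | Whole trial | P(≥ 1 in an arm) | P(two arms differ by ≥ 2) | P(0 of 352) |
|---|---|---|---|---|---|
| 0.1% | 0.58 | 1.74 | 44% | 14% | 70% |
| 0.3% | 1.74 | 5.22 | 82% | 40% | 35% |
| 0.5% | 2.90 | 8.70 | 95% | 52% | 17% |
| 0.9% | 5.22 | 15.66 | 99% | 64% | 4% |

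The phase 2b result fits the lower part of the range better. That comparison is loose, because the documents do not give that study's bilirubin entry rule.

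**The case against.** The strongest reply is that a liver safety table should be sensitive. The rule is identical in all arms, allocation is 1:1:1 with a placebo arm alongside, and SAP 6.5.2.1 plans counts and percentages without a test. Raised ALT or AST is allowed at entry only with normal bilirubin, so a Gilbert's woman with raised TBL should enter with normal transaminases. If she reaches a combined row, her transaminase has normally risen to above 3 × ULN, which the table ought to show. Change from baseline and shifts are summarised nearby, and independent hepatologists review cases that meet the liver withdrawal criteria (Protocol 10.2). All of this stands. It argues for keeping the unrestricted counts, but it does not justify counting a pre-dose sample as on-treatment, and case review does not alter the table.

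Four stronger readings are tempting and are not supported:
- **Every liver row is contaminated by entry values.** Step 2 shows otherwise for ALT, AST and ALP.
- **Eligibility is never checked on Day 1.** Table 1 marks the entry criteria at Randomization as well as Screening, and Exclusion 11 names no visit. The documents do not say whether Day 1 results are known before dosing.
- **The combined rows are Hy's Law rows that misclassify women with Gilbert's.** Protocol 12.5 does require "no evidence of intra- or extra-hepatic bilirubin obstruction (elevated ALP) or Gilbert's syndrome" for Hy's Law. However, the SAP does not label the rows that way, and TBL > 2 × ULN with ALT or AST > 3 × ULN also matches the protocol's severe liver abnormality, which has no Gilbert's exception.
- **The inflation equals all women with Gilbert's who exceed 2 × ULN at any visit.** A Week 12 value is a genuine on-treatment value, and the rates needed for such a figure are not in the documents.

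**Conclusion.** The point holds. As written, SAP 6.5.2.1 can count a pre-drug value as an on-treatment liver finding, in conflict with the SAP's own baseline and visit windows. The practical exposure is the TBL > 2 × ULN row and the bilirubin half of the combined rows.

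A reader might infer that the comparison with placebo is biased. It is not expected to be: randomisation spreads these women across arms on average. What remains is inflated counts and chance imbalance in rare rows.

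The size is unknown. The 0.6 to 5.2 women per arm rest wholly on the assumed 0.1% to 0.9%. That the Day 1 safety chemistry is pre-dose follows from the general visit-day rule; no sentence says so for that sample alone.

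**What to change.** In SAP 6.5.2.1:
1. Use only samples taken after the first dose (Day 2 onward, matching laboratory window a), and define the denominator on the same samples.
2. Beside the unrestricted counts, give the TBL row and the combined rows restricted to women whose baseline TBL was not above that row's bilirubin cut (2 × ULN, or 1.5 × ULN in the row that uses it). Step 1 alone is not enough, because bilirubin raised before drug can stay raised.
3. In the combined rows, flag or show separately women with Gilbert's syndrome or baseline TBL > ULN, with their direct bilirubin, which is already in the liver panel (Protocol 5.4.3). This covers a woman who starts below the cut and drifts over it, whom step 2 still counts.

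While editing, state which of the three combined rows the same-day rule covers.

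The cost is SAP wording and slightly longer tables. No new data are needed, and because the unrestricted counts stay, the restricted ones hide no signal in post-dose values.

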Endpoint	Variable that pertains to the efficacy or safety evaluations of a study. NOTE: Not all endpoints are themselves assessments since certain endpoints might apply to populations or emerge from analysis of results. That is, endpoints might be facts about assessments (e.g., prolongation of survival).
Enroll	To register or enter a subject into a clinical trial. NOTE: Once a subject has received the study drug or placebo, the clinical trial protocol applies to the subject.
Intervention	The investigational product under investigation to evaluate the effect on specified outcomes of interest (e.g., health-related quality of life, efficacy, safety and pharmacoeconomics).
Investigational period	This portion of the study refers to the time that a subject is receiving treatment (investigational product or placebo). This period of time is when major interests of protocol objectives are observed and continues until the last assessment is completed after final administration of the investigational product or placebo.
Follow-up period	Period of time after the last assessment of the protocol. Follow-up observations for sustained adverse events and/or survival are conducted during this period.
Randomization	The process of assigning subjects to treatment or control groups using an element of chance to determine assignments in order to reduce bias.
Rescreen	Subject can rescreen up to 1 time with the approval of the medical monitor, which will result in a new 35-day screening window. The subject will be entered as a new subject in the interactive response technology.
Retest	Subject can retest up to 1 time with approval from the medical monitor within the current 35-day screening window. The subject will retain the same subject identification number.
Screening	A process of active consideration of potential subjects for randomization in a study. NOTE: This is conducted after the subject signs the informed consent and agrees to be evaluated for study participation.
Screen failure	Potential subject who did not meet 1 or more inclusion criteria or met 1 or more exclusion criteria required for participation in a study and was not randomized.
Screening period	Period of time before entering the investigational period, usually from the time when a subject signs the consent until just before the test drug or comparative drug (sometimes without randomization) is given to a subject.

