Across the completed phase 1 and 2a studies, there have been a small number of mild, transitory transaminase elevations observed both in patients/subjects who received either fezolinetant or placebo. There were no incidences of raised TBL and none of the patients/subjects experienced associated symptoms. In the recently completed phase 2b study ESN364_HF_205, transitory increases in transaminase enzymes, ALT/aspartate aminotransferase (AST), have been reported in 7 subjects between 4 and 8 weeks after start of study treatment and in 2 unique subjects during study follow-up. Subjects were reported to be asymptomatic throughout and there was no evidence of functional liver impairment. Although there were cases with evidence of significant underlying hepatic conditions and other confounding factors, independent expert review of the cases that met a stopping rule concluded that the study drug was probably the cause of the increased transaminase levels. In all cases, transaminase enzyme levels rapidly decreased, in 2 cases during continuing treatment with study medication.

Based on cases of increased AST and ALT > 5 × ULN in the phase 2b study ESN364_HF_205 that were assessed by external hepatic experts as related to the use of fezolinetant, liver injury has been categorized as an important potential risk. Monitoring of liver parameters is incorporated in the design of this protocol, including individual patient stopping rules and liver assessment per [[Section 12.5](#)]. Increased transaminases have not been observed at the dose selected for this study, i.e., 30 mg fezolinetant once daily [[Section 2.2.2 Dose Rationale](#)].

Severe thrombocytopenia has been reported in non-clinical studies but not in clinical studies and has been categorized as an important potential risk. To date, 1 clinical case of mild, pre-existing, thrombocytopenia has been reported (in phase 2a Study ESN364_HF_204). Platelet counts are included in the hematological monitoring during the course of the study.

Circumoral paresthesia has been reported by several subjects taking fezolinetant. Considering the reported cases in the phase 1 studies (ESN364-CPK-101 and ESN364-CPK-102) the occurrence of circumoral paresthesia is dose dependent for both intensity and duration,

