7.6.2 Laboratory Assessments

For quantitative laboratory measurements descriptive statistics will be used to summarize results and change from baseline for subjects in the SAF by treatment group and time point.

Shifts relative to normal ranges from baseline to each time point during treatment period in lab tests will also be tabulated. Laboratory data will be displayed in listings.

Number and percentage of subjects with platelets $< 150 \times 10^9/L$ will be separately summarized for each treatment group. The liver safety assessments will be summarized by the categories below based on the measurements from ALP, ALT, TBL, AST and their combination. These parameters will be based on measurements from a central laboratory.

The subject's highest value during the treatment period will be used.

- $ALT > 3 \times ULN, > 5 \times ULN, > 10 \times ULN, > 20 \times ULN$
- $AST > 3 \times ULN, > 5 \times ULN, > 10 \times ULN, > 20 \times ULN$
- $ALT \text{ or } AST > 3 \times ULN, > 5 \times ULN, > 10 \times ULN, > 20 \times ULN$
- $ALP > 1.5 \times ULN$
- $TBL > 2 \times ULN$
- $(ALT \text{ or } AST > 3 \times ULN) \text{ and } TBL > 2 \times ULN$
- $(ALT \text{ or } AST > 3 \times ULN) \text{ and } ALP < 2 \times ULN \text{ and } TBL > 2 \times ULN$

The last 2 criteria where 2 or more parameters are evaluated will be with the measurements on the same day or up to 1 day apart.

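### The liver threshold table closes at last dose + 1 day, so later values cannot enter any row; add a second table running through Visit 16

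*SAP*

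**What the plan says.** **The table.** SAP 6.5.2.1 counts women above cut-offs from 3× to 20×ULN for ALT and AST, above set multiples for ALP and bilirubin, and in three combined ALT/AST-bilirubin rows. The value used is the "highest value during the investigational period (from day of first dose of study drug until last dose of treatment period + 1 day". The denominator follows the same period: "The denominator for each criterion will be the number of subjects who have at least one value during the double-blind investigational period". The primary liver analysis adds local results taken because of COVID-19. The secondary uses central results and drops COVID-19-affected data. Neither states a different window.

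**The general safety rule.** SAP 6.5 says: "Except for adverse events and follow-up visit data, only data up to one day after the last dose date will be considered for the analyses". Follow-up visit data are thus exempt from the general cut-off, but 6.5.2.1 sets its own closed period and does not take up the exemption.

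**The protocol.** Section 7.6.2 says of the same table that the subject's "highest value during the treatment period will be used". The Definition of Key Study Terms describes the investigational period first as time on treatment, and then says it "continues until the last assessment is completed after final administration of the investigational product or placebo".

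**Sampling after the last dose.** Protocol 12.5 asks for a retest within 72 hours of notification and adds: "Subjects who develop a signal for liver injury will be monitored every 2 to 4 weeks if the study drug is discontinued". Table 1 schedules clinical laboratory tests at Week 55.

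**The concern.** Protocol 1.5 classes liver injury as an important potential risk, and long-term safety is a primary objective. This table is the plan's by-arm count of peak enzyme values against multiples of ULN, and it holds the rows that would show a potential Hy's law case.

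The protocol ends treatment in women with marked liver signals and then keeps sampling them. The table's window closes one day after the last dose, which is when that extra sampling begins. If enzymes or bilirubin go on rising after the drug is stopped, the higher and combined rows undercount severity. The undercount would be larger in an arm where more women stop for liver tests, so any bias would run toward showing no liver signal.

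**Working it through.** **1. A woman who stops on a liver signal.** Assume the last dose is on the day of notification, N.
- Table window closes: N + 1.
- Retest allowed within 72 hours: up to N + 3, so it can fall outside the window.
- First off-drug monitoring sample at 2 to 4 weeks: N + 14 to N + 28, always outside.

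Take a woman at 4×ULN on drug whose ALT passes 8×ULN at N + 3. She stays in the > 3× row and does not enter the > 5× or > 8× rows. If that sample also shows bilirubin > 2×ULN, she is missing from the combined rows.

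One limit applies. The SAP pairs values on the same day or up to 1 day apart (worded for its last two criteria). Where that rule applies, a longer window captures a bilirubin rise only if ALT or AST is still > 3×ULN at about the same time.

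**2. A completer.** Protocol Table 1 puts the last dose on the day before the Week 52 visit.
- Last dose: Day 364.
- Window closes: Day 365, so the Week 52 sample is counted.
- Week 55: Day 386, and 386 − 364 = 22 days after the last dose. With ± 3 days this is 19 to 25 days.
- Adverse event window closes: 364 + 21 = Day 385.

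Week 55 is outside the liver table and can also fall after adverse event collection closes. A woman with normal values on drug and a first elevation at Week 55 is in the denominator but not the numerator.

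**3. By-visit summaries.** SAP 6.10.1 assigns all data beyond last dose + 1 day to the follow-up visit and keeps the value nearest Day 386. For a woman who stopped well before then, that is normally her latest value, by which time a peak may have resolved.

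**4. The phase 2b count.** Protocol 1.5 reports elevations "in 7 subjects between 4 and 8 weeks after start of study treatment and in 2 unique subjects during study follow-up". 7 + 2 = 9, which matches the nine subjects with ALT or AST > 3×ULN in Protocol 1.4.2 and 2.2.2. If both follow-up cases lay beyond last dose + 1 day, this rule would have counted 7 of 9 and missed 2/9 = 22% (Clopper-Pearson 95% CI 2.8% to 60.0%). One was 3 weeks after the last dose; the day of the other is not given. If only one is lost, the figure is 1/9 = 11%.

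**5. What such a loss would do.** The plan's detection table is P(X ≥ r) with X ~ Binomial(580, p). All 27 cells reproduce to two decimals; for example, p = 0.90% gives 89.38%, 96.69% and 99.47% for r = 3, 2 and 1. Replacing p by p × (1 − loss), for an assumed true rate of 0.90%:

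| Loss | Rate seen | P(≥ 3 cases in an arm) |
|---|---|---|
| none | 0.90% | 89.38% |
| 2.8% | 0.87% | 88.25% |
| 11% | 0.80% | 84.27% |
| 22% | 0.70% | 77.16% |
| 60% | 0.36% | 34.72% |

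At a true rate of 0.50% and a 22% loss, the rate seen is 0.39%. P(≥ 3) falls from 55.46% to 39.23% and P(≥ 1) from 94.54% to 89.56%.

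**6. Could the loss differ by arm?** In phase 2b five women on fezolinetant and none on placebo stopped for liver enzymes (Protocol 1.4.2). Table 2 of the protocol gives 312 randomized to fezolinetant and 44 to placebo. 5/312 = 1.6%, and at that rate the chance of none among 44 is (1 − 5/312)^44 ≈ 49%. A difference is plausible but not shown.

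**The case against.** **Other outputs count these events.** A reader might infer that liver events after stopping are not counted anywhere. The documents do not support that. Liver test elevation is an adverse event of special interest, reported with rate, odds ratio and exact confidence intervals (SAP 6.5, 6.5.1). Treatment-emergent events run to 21 days after last dose. Discontinuation for liver enzymes is itself a serious adverse event (Protocol 5.8.2), as is a severe liver abnormality without another cause (Protocol 12.5). Adverse events are a primary endpoint; laboratory tests are secondary. This stands, and it reduces the weight of the point. It does not close the gap: event counts depend on reporting and are not graded by multiples of ULN, Week 55 can fall after day 21, and the hepatologists' committee reviews individual cases rather than giving rates by arm.

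**The SAP follows the protocol.** A reader might also infer that the SAP contradicts the protocol. For this table it does not: Protocol 7.6.2 says treatment period. The key-terms definition is mixed, and the SAP states its own window in brackets. With a terminal half-life of 4 to 6 hours (Protocol 1.3.2), one day is a coherent on-treatment window. It should stay.

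**Phase 2b does not show carry-over.** Of the two follow-up cases, one woman had normal values throughout the study and her elevation was judged unlikely related; no attribution is given for the other. Protocol 1.5 says enzymes fell rapidly in all cases, and Protocol 1.4.2 reports no bilirubin > 2×ULN. The sequence of stopping and then worsening therefore has no example in those data.

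**Most stopped women still appear.** Every mandatory transaminase rule in Protocol 6.1 needs a value above 3×ULN. A woman stopped on on-treatment results is already in that row; what is lost is her later re-grading.

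**Conclusion.** The point holds as a limit of one table. The single and combined liver rows cannot reflect anything after last dose + 1 day, although the protocol schedules samples then, and no other planned output gives the post-treatment peak by arm. The direction of any error is toward undercounting.

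Its size cannot be stated from the documents. The 22% rests on 2 of 9 cases, assumes both fell outside the window, and comes from a 12-week study in which 7 of the 9 cases were at total daily doses of 120 mg or more. This trial uses 30 and 45 mg. The binomial figures show what a given loss would do, not what will happen. It might also be inferred that one missed combined case would overturn the trial's conclusion; no decision rule is attached to this table, so that does not follow.

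This should be fixed because it is cheap and the rows concern a named risk. It does not invalidate the planned analysis.

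**What to change.** In SAP 6.5.2.1:
- Keep the last dose + 1 day table and label it on-treatment. It still meets Protocol 7.6.2.
- Add the same table by arm, labelled on-study, with each woman's highest value from first dose through Visit 16, including unscheduled and off-drug liver retests. Use it for single and combined criteria, with the existing pairing rule and a denominator from the same period.
- State whether retests later than Visit 16 count. After early stopping, Visit 16 falls about 3 weeks after the last dose, while a monitoring sample may come at 4 weeks.
- Define both periods explicitly, so that the term investigational period does not clash with the protocol's key terms.

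The cost is SAP wording and one rerun of an existing table on data the protocol already collects. Longer windows have precedent in this SAP: ultrasound, DXA and biopsy all run to 30 days after treatment. The drawback is that some off-drug elevations with other causes will be counted, in all arms including placebo; the placebo arm shows how common these are.
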